5.5. Rescue Treatment

In the event of hemodynamic collapse, the following emergency supportive and therapeutic measures can be provided at the discretion of the investigator and responsible clinical team:

- Inotropic or vasopressor agents
- Additional rescue peripherally-administered systemic fibrinolytic therapy
- Surgical pulmonary embolectomy
- Catheter-assisted embolectomy including catheter directed thrombolysis and embolectomy
- IVC filters: The insertion of IVC filters is discouraged unless the subject develops a contraindication to therapeutic dose systemic anticoagulation or if the subject suffers recurrent PE despite therapeutic levels of anticoagulation.
- ECMO

5.6 SAFETY ASSESSMENTS

Adverse events/SAEs, vital signs, significant physical examination findings, and results of clinical laboratory tests will be assessed throughout the study. A local laboratory will perform the laboratory

analyses and will provide reference ranges for these tests. The following clinical laboratory tests will be performed:

Hematology

Hemoglobin Hematocrit Platelet count

Liver Function Tests

ALT AST Total Bili

Chemistry Creatinine

Other Analyses

Pregnancy test (WOCBP only: screening)

6. DATA COLLECTION, MANAGEMENT AND ANALYSIS

6.1. DATA COLLECTION METHODS

After obtaining consent, all subjects are assigned a study-specific ID upon enrollment, which will be used in lieu of PHI to obtain patient data for SAFE-LYSE. The study-specific ID will be linked to the subject's medical record number. The information will be stored in a password protected file on a secure server, behind CSMC's firewall and only accessible to select study investigators.

When a physician refers patients to the SAFE-LYSE study, study staff will pre-screen the patient for eligibility. If the patient qualifies, the PI or sub-investigator will introduce the study and review the informed consent with the patient. If the patient agrees to participate, the consent form will be signed and the patient will be randomized. The research pharmacy is notified and will begin to prepare study drug or placebo as assigned. In the meantime, appropriate study staff will collect necessary labs, administer questionnaires, and complete case report forms at certain timepoints per protocol. All imaging will be de-identified and transferred to the Syntactx imaging core laboratory for evaluation. Upon discharge, study staff will coordinate attendance at Day 30, 180 and 365 follow-up visits. Study staff will also conduct interim phone calls to assess for AE's and administer questionnaires per protocol at Day 90 and 270.

6.1.2. WITHDRAWAL

Subjects may withdraw from the study for any reason at any time. The investigator also may withdraw subjects from the study in order to protect their safety and/or if they are unwilling or unable to comply with required study procedures. Subjects also may be withdrawn if BMS/ Pfizer Alliance or government or regulatory authorities terminate the study prior to its planned end date.

All data collected prior to withdrawal will remain part of the study. Every effort will be made to have the subject return to the clinic to obtain final study assessments.

6.2. DATA MANAGEMENT

The Investigator will ensure that the records and documents pertaining to the conduct of the study and the distribution of the investigational product are complete, accurate, filed and retained. Examples of source documents include: hospital records; clinic and office charts; laboratory notes; memoranda; subject's diaries or evaluation checklists; dispensing records; recorded data from automated instruments; copies or transcriptions certified after verification as being accurate copies; CTA reports; and records kept at the pharmacy and the laboratories, as well as copies of CRFs.

6.2.1. DATA FORMS AND DATA ENTRY

Data will be collected via case report forms (CRF) and entered into a research database maintained in REDCap (Research Electronic Data Capture). This data will be electronically verified through use of programmed edit checks specified by the clinical team. Discrepancies in the data will be flagged in REDCap and corrected by the study team. An audit trail within REDCap will track all changes made to the data.

CT and Echo DICOM images will be transmitted to the imaging core laboratory, Syntactx. A central reader will review the images and complete a case report form. Syntactx will read the images in bulk at the end of the study.

6.2.2 DATA TRANSMISSION AND EDITING

The data entry fields in REDCap will resemble the CRFs used to capture study data. Data integrity will be enforced through a variety of mechanisms. Referential data rules, valid values, range checks, and consistency checks against data already stored in the database will be supported. Checks will be applied at the time of data entry into a specific field and/or before the data is written into the database. Modifications to the data written to the database will be documented through either the data change system, an inquiry system, and/or the electronic audit trail created in REDCap for entries and changes. Data entered into the database will be retrievable for view in REDCap. The type of activity that an individual user may undertake is regulated by the privileges associated with his/her user identification code and password.

6.2.3 DATA DISCREPANCY INQUIRIES AND REPORTS TO CORE COORDINATING CENTERS

Additional errors will be detected by programs designed to detect missing data or specific errors in data. These errors will be summarized along with detailed descriptions for each specific problem in Data Query Reports. The research staff who receives the inquiry will respond by checking the original forms for inconsistency, checking other sources to determine the correction, and/or modifying the original form by entering a response to the query. The CDCC will be responsible for making appropriate corrections to the original paper forms whenever any data item is changed. Written documentation of changes will be available via electronic logs and audit trails.

6.2.4 SECURITY AND BACK-UP OF DATA

Study-related reports, documents and trackers will be stored on a HIPAA compliant secure server on a password-protected computer. The research team will ensure that records and documents pertaining to the conduct of the study are complete, accurate, filed and retained. A complete back-up of the primary database will be performed once per month.

6.3. DATA MONITORING

6.3.1. FORMAL COMMITTEE

A Data Monitoring Committee (DMC) will be assembled to assess safety endpoints. The Board will be comprised of 3 non-study personnel who are experts in the field of Pulmonary Medicine. The Board will

meet after the first 10 patients complete Day 30. The DMC will be independent from the CSMC, BMS and competing interests. A charter with further details will be available.

6.3.2. HARMS

A rigorous screening process will be utilized to verify eligibility. This will include reviewing the imaging diagnosis of PE (to ensure that subjects without acute PE are not inadvertently enrolled in the study), performing a detailed history and physical examination (to ensure that enrolled subjects truly fulfill all eligibility criteria), and carefully reviewing the results of laboratory testing (in particular, hematocrit, platelet count, INR, and creatinine clearance).

During study drug treatment period, the subject will be monitored during the infusion and the infusion will be stopped if bleeding occurs. To reduce the risks associated with the CTA, we will ascertain that the subject has no history of allergic reaction to the contrast and we will make sure their creatinine clearance is adequate.

During the follow-up period, changes in health status will be evaluated by the study doctor and reported as deemed appropriate.

6.3.3. AUDITING

Through the combination of our use of REDCap with its electronic error detection, QA/QC plan, and regular site monitoring, we will ensure the quality and completeness of data in this trial.

7. STATISTICAL CONSIDERATIONS

7.1. SAMPLE SIZE DETERMINATION

7.1.1. EFFICACY

The following information was prepared in collaboration with the Cedars-Sinai Biostatistics Department. The primary outcome is mean change in percentage of clot lysis by RMMS from the 24 hour CTA after 24 mg of systemic (IV) tPA + standard anticoagulation therapy compared to the baseline CTA.

- Statistical Analysis: The main objective is to determine the mean change in clot lysis by RMMS from baseline to 24 hours in treatment A (systemic [IV] tPA + IV unfractionated heparin). Data will be presented as frequency (percentage, %) for categorical variables and mean (± SD, standard deviation) for continuous variables. Profile plots with mean RMMS(± SE, standard error) at baseline and 24 hours will be displayed. The post-treatment RMMS score at 24 hours as an outcome variable will be modeled using a generalized additive model for location, scale and shape [26, 27] after adjusting for the treatment group and the baseline RMMS score [28] to examine if there is a difference in the change in RMMS from baseline to 24 hours between two treatment groups. The underlying assumptions will be checked using residuals [29]. Statistical analyses will be conducted using R package version 3.4.1 [30] with two-sided tests and a significance level of 0.05.
- Sample Size Justification: Statistical power was estimated with a two-sided two-sample equalvariance t-test. A mean difference of at least 15 percentage units between baseline and posttreatment A will be clinically meaningful. According to a previous study [22], the baseline RMMS was 21.14 units, thus a decrease of 15% from the amounts is 3.171 units in RMMS. Using the standard deviation of the difference in RMMS to 48h post-procedure from the baseline of 2.7 units obtained from the same study, 17 patients per group (34 total) achieve 99.5% power, to detect a

difference of 15 percentage units (i.e., 3.171 units difference in RMMS) between the baseline CTA and 24 hour post-treatment CTA in treatment A with 5% significance level using a two-sided two-sample equal-variance t-test.

A secondary outcome is mean change in percentage of clot lysis by RMMS from the 24 hour CTA after 24 mg of systemic (IV) tPA + standard anticoagulation therapy (treatment A) compared to that of the 24 hour CTA after standard anticoagulation therapy alone (treatment B).

- Statistical Analysis: We will also compare the RMMS at 24 hours for treatment A, with that of treatment B (saline placebo + IV unfractionated heparin) as a secondary outcome. Data will be analyzed and presented in the same way as the primary outcome.
- Sample Size Justification: Statistical power was estimated in the same way as the primary outcome.
 17 patients per group achieve 91% power to detect a difference of 15 percentage units between 24 hour post-treatment CTAs of treatments A and B.

Another *secondary outcome* is change from baseline RV/LV ratio by chest CTA expressed as percentage change from baseline.

- Statistical Analysis: Statistical analysis for the seconday outcome will be similar to the primary outcome.
- Sample Size Justification: Statistical power was estimated with a two-sided two-sample equalvariance t-test. A previous study [22] showed that the mean and standard deviation of percentage change in RV/LV ratio from baseline to 48 hours are 26 and 22.7, respectively. Assuming these hold for our study , data from 17 patients per group (34 total) achieve 90% power to detect a mean difference of 26 percentage units between the two treatments with 5% significance level using a two-sided two-sample equal-variance t-test.

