	 creatinine clearance < 30 mL/min platelets < 100 thousand/µL INR > 1.4 Alanine transaminase (ALT) or aspartate transaminase (AST) ≥ 2 times upper limit of normal (ULN) Total bilirubin (TBL) ≥ 1.5 times ULN (except due to confirmed Gilbert's syndrome) Patient is pregnant (positive pregnancy test; women of childbearing capacity must be tested prior to enrollment) or breast feeding Patient who is a prisoner, or if subject who becomes compulsory detained Active cancer defined as diagnosis of cancer within six months before the study inclusion, or receiving treatment for cancer at the time of inclusion or any treatment for cancer during 6 months prior to randomization, or recurrent locally advanced or metastatic cancer. Known allergy, hypersensitivity or thrombocytopenia from heparin, tPA, or apixaban or iodinated contrast except for mild-moderate contrast allergies for which steroid pre-medication can be administered within 12 hours prior to the CTA. HIV/AIDS Weight >130 kg or < 40 kg on day of randomization
Sample Size	In this trial, 40 subjects (20 per arm) will be randomized into two treatment arms, 1) 24 mg IV PA + standard anticoagulation therapy (IV heparin) vs 2) saline placebo + standard anticoagulation therapy (IV heparin), using a computer program at Cedars-Sinai Medical Center in Los Angeles, California. Additional subjects may be consented to compensate for screening failures and/or treated patients who lack sufficient data. Approximately 40 subjects will be enrolled into the study, with approximately 20 subjects in each arm. A subject will be deemed evaluable if he/she has valid CTA imaging evaluations at both baseline and $\leq 24h \pm 8$ hours post-end of infusion and successfully completed administration of study drug infusion. Randomized subjects who do not complete blinded study drug administration (i.e., subjects who stop the IV infusion early due to AEs) will still be followed for safety through Day 30.

	The planned sample size is based on a two-sided two-sample equal-variance t-test. A previous study [19] showed that the mean and standard deviation of percentage change in RV/LV ratio from baseline to 48 hours are 26 and 22.7, respectively. Assuming these hold for our study , data from 17 patients per group (34 total) achieve 90% power to detect a mean difference of 26 percentage units between the two treatments with 5% significance level using a two-sided two-sample equal-variance t-test.

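### The 90% power for RV/LV uses a change from baseline as the tPA-versus-placebo difference, with no heparin-arm change stated

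*Combined protocol and SAP*

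**What the plan says.** The RV/LV paragraph of Section 7.1.1 reports from a previous study, cited as [22], that "the mean and standard deviation of percentage change in RV/LV ratio from baseline to 48 hours are 26 and 22.7, respectively". It continues "Assuming these hold for our study" and concludes that 17 per group, 34 in all, would "achieve 90% power to detect a mean difference of 26 percentage units between the two treatments". The calculation is for a two-sided t-test on two samples with equal variances, at the 5% level.

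The Sample Size row of the synopsis opens with "The planned sample size is based on a two-sided two-sample equal-variance t-test" and then gives the same calculation and no other. There the source is cited differently: "A previous study [19] showed that the mean and standard deviation of percentage change in RV/LV ratio".

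The comparator is a placebo infusion plus intravenous heparin. Section 1.2.2 defines the endpoint as the CTA-measured change in RV/LV to 24 ± 8 hours, compared with placebo. Section 7.1.3 enrols 20 per arm to end with 17. Neither the synopsis nor Section 7 states an expected RV/LV change for the heparin arm.

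**The concern.** A mean change from baseline describes what happens over time in one group. The power of a two-arm comparison depends on how much more one arm changes than the other. The plan moves from the first quantity to the second without a step between them. If the tPA arm is expected to change by 26 points and the arms are also expected to differ by 26, the heparin arm is implicitly expected to change by 0. That value is neither stated nor justified.

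This matters because the synopsis rests the sample size on this calculation, and because the overall objective in Section 1.2 is a comparison with standard care. If the real difference between arms is smaller than 26, a non-significant RV/LV result could be read as evidence of no effect from a comparison with 90% power, when the power was much lower.

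**Working it through.** **Inputs from the documents.** Treated change 26 and SD 22.7 (Section 7.1.1 and synopsis); n = 17 evaluable per arm (Section 7.1.1); 20 enrolled per arm (Section 7.1.3); two-sided 5% two-sample t-test with equal variances.

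**Input not in the documents.** The heparin-arm improvement c, in percentage points. It is an assumption, so it is varied.

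**Formulas.** Between-arm difference d = 26 − c. Noncentrality λ = d / (SD × √(2/n)). Power is the probability that a noncentral t variable with 2n − 2 degrees of freedom and noncentrality λ falls beyond the two-sided 5% critical values.

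**Step 1: reproduce the plan's figure.** With n = 17, SD × √(2/n) = 22.7 × 0.3430 = 7.786. With d = 26, λ = 26 / 7.786 = 3.34 on 32 degrees of freedom. Power is 89.9%, which matches the stated 90%. (The normal approximation gives 91.6%.)

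**Step 2: find the slack.** Solving for the difference that gives exactly 90% power:
- n = 17: d = 26.03. Against a treated change of 26 this leaves 26 − 26.03 = −0.03, so there is no room for any heparin improvement.
- n = 20: d = 23.88. This leaves 26 − 23.88 = 2.12 points.

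**Step 3: vary the heparin change.** With n = 20, SD × √(2/n) = 22.7 × 0.3162 = 7.178.

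| Heparin change c (assumed) | d = 26 − c | λ, n = 17 | Power, n = 17 | λ, n = 20 | Power, n = 20 |
|---|---|---|---|---|---|
| 0 | 26 | 3.34 | 89.9% | 3.62 | 94.2% |
| 2 | 24 | 3.08 | 84.8% | 3.34 | 90.3% |
| 5 | 21 | 2.70 | 74.4% | 2.93 | 81.3% |
| 10 | 16 | 2.05 | 51.3% | 2.23 | 58.4% |

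**Step 4: vary the SD.** If the effective SD were 20 instead of 22.7 (an illustrative value, not from the documents), power with 17 per arm would be 95.7%, 84.3% and 61.9% for c = 0, 5 and 10.

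**The case against.** **It is only a detectable difference.** The sentence names a difference between the two treatments, and power for a 26-point difference is 90% whatever the heparin arm does. A treated change of 31 with a heparin change of 5 gives the same 90%. This stands as arithmetic. It follows that one cannot say the 90% applies only when heparin patients do not change. But the plan does not choose 26 as a difference worth detecting. It takes 26 from an observed change from baseline and assumes that it carries over, so 26 is presented as an expected value, and it was observed as a different quantity.

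**The trial enrols 20 per arm.** The extra three are an allowance for attrition. If none is lost, about 2 points of heparin improvement can be absorbed. At 5 points the power is still only 81%.

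**The analysis adjusts for baseline.** Section 7.1.1 says that RV/LV will be analysed much as the primary outcome is, and that model includes the baseline value. Some power may be recovered. The documents give no correlation, so the amount cannot be stated, and the plan's own power figure takes no credit for it.

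**Heparin may do little this early.** Section 1.1 reports no difference on heparin alone, but for pulmonary artery pressure and cardiac index two hours after infusion began. That does not support zero RV/LV change at 24 hours.

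**It is a secondary outcome.** This is true, and Section 7.1.1 powers the primary RMMS outcome separately. That limits the consequence, although the synopsis gives no other basis for the sample size.

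**A reader might extend the point to RMMS**, where Section 7.1.1 says "17 patients per group achieve 91% power to detect a difference of 15 percentage units" between the arms. The documents do not support that. The primary hypothesis and Section 7.1.1 treat 15% as a minimum and a clinically meaningful threshold, not as the expected effect of tPA. Lysis of 20% against 5%, or 25% against 10%, also differs by 15 points, so the 91% does not require zero lysis on heparin.

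**Conclusion.** The concern holds for RV/LV. The calculation is correct, but its main input is a change from baseline used as a difference between arms, so the 90% is not supported by the source given for it. Under the plan's own values (treated change 26, SD 22.7, 17 evaluable per arm), the heparin arm would have to change by about zero. Improvements of 5 or 10 points on heparin would bring power to 74% or 51%, or to 81% or 58% with all 20 per arm evaluable.

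These figures rest on an unadjusted t-test and on assumed heparin changes. They show how sensitive the power is and do not estimate the true power. A larger treated change or a smaller SD would leave more room. Two features of the source add uncertainty. Its change is to 48 hours, while this trial measures at 24 ± 8 hours. And the two citations point to different studies: by its title, [22] is a randomised trial of the duration of a catheter thrombolysis procedure, while [19] is a trial of thrombolysis in moderate pulmonary embolism. That the 26 comes from a treated group is inferred from those titles; that it is a change from baseline is stated in both places.

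**What to change.** In the synopsis and in Section 7.1.1:

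1. State that 26 (SD 22.7) is a percentage change from baseline to 48 hours, say in which group it was observed, and reconcile the citation ([19] in one place, [22] in the other).
2. Give an expected RV/LV change for the heparin arm at 24 hours with its source. If there is none, give a range labelled as assumed.
3. Restate the power for the resulting between-arm difference. Alternatively, present 26 only as the difference detectable with 90% power at 17 per arm, without suggesting that it is the expected effect.

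The cost is a less favourable stated power. No extra patients and no change to the analysis are needed.

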7.1.2. SAFETY

 Sample Size Justification: The main safety risk is bleeding in a critical site. The full list of primary and secondary safety endpoints is presented in Section 1.3.4. We expect that the incidence of bleeding will be 5% or less at Day 30. Table 1 shows two-sided exact confidence intervals (Clopper-Pearson) at 95% level for selected incidences of bleeding with a sample size of 17 patients.

Table 1.95% Exact Confidence IntervalWidth, Lower Limit, and Upper Limit for selected incidences of bleeding							
Incidences Confidence Lower Upper Width Limit Limit							
0.01	0.212	0	0.212				
0.02	0.229	0	0.229				
0.03	0.244	0	0.245				
0.04	0.259	0	0.26				
0.05	0.274	0.001	0.274				

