1.2.3 SAFETY ENDPOINTS

Primary Safety Endpoints

The primary safety endpoint is major bleeding within 72 hours after initiating systemic tPA infusion. Major bleeding events will be defined by Global Use of Strategies to Open Occluded Arteries (GUSTO) criteria for severe or life threatening bleed. This includes:

- Intracerebral hemorrhage
- Resulting in a substantial hemodynamic compromise requiring treatment

Secondary Safety Endpoints

- GUSTO severe or life threatening bleeding within 30, 180 and 365 days
- Need for rescue therapies such as full dose systemic thrombolysis, catheter-directed thrombolysis, catheter directed embolectomies, or surgical embolectomy within 30 days
- Ischemic or hemorrhagic stroke within 30 days
- All-cause mortality at Day 365
- Symptomatic PE recurrence: The patient must have signs and symptoms of recurrent PE in addition to objective confirmation such as a new filling defect on chest CTA or pulmonary arteriogram at Day 365
- Hemodynamic decompensation within 30 days as defined as a systolic blood pressure <90mmHg and/or need for vasopressor support.

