7.1.3. ATTRITION

The determined sample size is 17 subjects per arm (34 total), but we will enroll 20 per arm (40 total) to allow for potential attrition.

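### Table 1's exact bleeding intervals are computed for fractions of a patient (0.17 to 0.85 events in 17), so no row can occur; whole-event rows should replace them

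*Combined protocol and SAP*

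**What the plan says.** Section 7.1.2 (Safety) names bleeding in a critical site as the main risk and states: "We expect that the incidence of bleeding will be 5% or less at Day 30". It then presents Table 1 as "two-sided exact confidence intervals (Clopper-Pearson) at 95% level for selected incidences of bleeding with a sample size of 17 patients". The five rows are for incidences of 0.01, 0.02, 0.03, 0.04 and 0.05, each with an interval width, a lower limit and an upper limit. The first row reads "0.01 0.212 0 0.212" and the last "0.05 0.274 0.001 0.274". No event counts are given, and nothing says that the rows are interpolated or averaged over possible outcomes.

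Section 7.1.3 explains the 17: it is the required number per arm, and "we will enroll 20 per arm (40 total) to allow for potential attrition". Section 1.2.3 sets the time point of the main safety outcome: "The primary safety endpoint is major bleeding within 72 hours after initiating systemic tPA infusion". It also lists severe or life-threatening bleeding within 30 days as a secondary safety endpoint.

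Two other places bear on the denominator:
- The Sample Size entry of the synopsis says that randomized subjects who do not complete the infusion are still followed for safety through Day 30. Section 3.5 likewise keeps subjects whose alteplase is stopped in follow-up.
- The stopping rules in section 3.5 equate a severe-bleed rate of 15% with three patients.

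**The concern.** A Clopper-Pearson interval inverts binomial tail probabilities for an observed whole number of events. With 17 patients the observed incidence can be 0%, 5.9%, 11.8% and so on; 1% to 5% cannot be observed. A table that calls its entries exact intervals at those incidences therefore shows results that the trial cannot produce.

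Table 1 is the only safety sample-size justification in section 7.1.2, in a trial whose rationale is less bleeding at a lower dose. A reader who uses it to learn what the trial will be able to say about bleeding gets figures that match neither zero events nor one event. The reader is also shown nothing for two or more events.

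**Working it through.** **Inputs.** From section 7.1.2: two-sided 95% Clopper-Pearson, n = 17, incidences p = 0.01 to 0.05. From section 7.1.3: 20 per arm enrolled.

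**Formula.** For x events in n patients, lower = Beta quantile(0.025; x, n − x + 1), set to 0 when x = 0; upper = Beta quantile(0.975; x + 1, n − x).

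**Step 1: reproduce the table.** Set x = 17p.

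| p | x = 17p | Lower | Upper | Width | Printed width, lower, upper |
|---|---|---|---|---|---|
| 0.01 | 0.17 | 0.0000 | 0.2124 | 0.2124 | 0.212, 0, 0.212 |
| 0.02 | 0.34 | 0.0000 | 0.2288 | 0.2288 | 0.229, 0, 0.229 |
| 0.03 | 0.51 | 0.00003 | 0.2445 | 0.2445 | 0.244, 0, 0.245 |
| 0.04 | 0.68 | 0.0002 | 0.2597 | 0.2594 | 0.259, 0, 0.26 |
| 0.05 | 0.85 | 0.0007 | 0.2743 | 0.2736 | 0.274, 0.001, 0.274 |

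Every row agrees to rounding. Whole counts, one-sided limits, and n = 20, 34 or 40 do not give the table.

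**Step 2: test the planning-table reading.** If each p were a true incidence, the natural planning quantity would be the width averaged over Binomial(17, p). The averages are 0.210, 0.224, 0.238, 0.251 and 0.264. The printed widths are 0.212, 0.229, 0.244, 0.259 and 0.274. They are close, but they are not the same quantity.

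**Step 3: attainable intervals.** For zero events the upper limit has a closed form: 1 − 0.025^(1/17) = 0.195 and 1 − 0.025^(1/20) = 0.168.

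| Events | n = 17 | n = 20 |
|---|---|---|
| 0 | 0 to 19.5% | 0 to 16.8% |
| 1 | 0.1% to 28.7% (rate 5.9%) | 0.1% to 24.9% (rate 5.0%) |
| 2 | 1.5% to 36.4% | 1.2% to 31.7% |
| 3 | 3.8% to 43.4% | 3.2% to 37.9% |

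**Step 4: size of the discrepancy at n = 17.** The lowest printed upper limit exceeds the zero-event limit by 21.2 − 19.5 = 1.7 percentage points. The highest falls short of the one-event limit by 28.7 − 27.4 = 1.3 points.

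**Step 5: what the table leaves out.** At a true incidence of 5% and n = 17, P(0) = 0.418 and P(1) = 0.374, so P(2 or more) = 1 − 0.418 − 0.374 = 0.208. About one trial arm in five would then have an upper limit of 36.4% or more, beyond anything tabulated.

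**Step 6: denominator.** Subjects who stop the infusion early stay in safety follow-up, so the number at risk of bleeding is closer to the number dosed than to the 17 left after attrition. The stopping rule's 15% as three patients implies 3 / 0.15 = 20.

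**The case against.** The strongest defence is that the text speaks of selected incidences next to an expected rate, so Table 1 may be meant as a planning aid over assumed rates and not as a list of possible results. On that reading the printed widths are slightly conservative, by at most 0.274 − 0.264 = 0.010. This limits the size of the problem but does not remove it: the table is labelled as exact intervals, does not mention averaging, and does not match the averaged widths.

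It is also fair to say that nothing rests on the table. The enrolment number comes from the efficacy calculations, and the bleeding stopping rules are already stated in whole patients. That stands.

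The use of 17 can be defended as the plan's own post-attrition size and as conservative. The documents define no safety analysis set, and the 20 implied by the stopping rule is also the total number of subjects at the interim analysis, so that rule supports 20 per arm without settling it. Rows for both denominators meet this objection.

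Three stronger readings are tempting and should not be adopted:
- A reader might infer that the Day 30 label is an error because the primary safety endpoint is at 72 hours. Severe bleeding within 30 days is a listed secondary safety endpoint, and the limits depend only on the count and n, so relabelling would change no number.
- A reader might infer that the plan claims it can confirm a rate of 5% or less. The text states an expectation, with no hypothesis or success criterion at 5%, and the printed upper limits above 20% already show that such a rate could not be confirmed.
- A reader might infer that the safety precision is badly misstated. At zero or one event the discrepancy is under 2 points.

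**Conclusion.** The point holds as a defect in a stated precision figure. Table 1 gives limits labelled exact for event counts of 0.17 to 0.85, and none of its rows is attainable with 17 patients. All five printed upper limits fall in the gap between the limits for 0/17 and 1/17, and outcomes of two or more events are missing. The practical effect is modest, and no enrolment number, stopping rule or efficacy analysis changes. The correction is still worth making because the table is the section's only safety justification and the repair is almost free.

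The arithmetic rests only on the method, confidence level and n stated in section 7.1.2. The preference for 20 as the main denominator assumes that all 20 planned subjects per arm are dosed and kept in the bleeding analysis. The follow-up provisions support this, but the plan does not state it.

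**What to change.** Replace Table 1 with whole-event rows for the dosed patients in an arm, using the n = 20 column above (0, 1, 2 and 3 events). The n = 17 column may be shown beside it, labelled as the post-attrition case. State which denominator the bleeding analysis will use.

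Add one sentence: with zero events in 20 patients the two-sided 95% upper limit is 16.8%, so a rate of 5% or less can be observed, but higher rates cannot be excluded. A note that the same limits apply to the 72-hour primary safety endpoint as well as to Day 30 would help but is optional.

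The cost is one table and one or two sentences, with no change to sample size, procedures, monitoring or stopping rules.
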